## Methods

---

### Study design and setting

A longitudinal mixed method study will be conducted in Harare City Health Department at three high volume clinics (BRIDH, Kuwadzana and Rujeko). All the clinics provide care as part of the Paediatric Opportunistic Infection and Antiretroviral Therapy program (OI/ART) and started conducting routine viral load testing in 2016. BRIDH has capacity for onsite VL testing. The three clinics are situated in the low-income and overpopulated residential suburbs which are ranked among the poorest residential areas in Harare (Mbare, Kuwadzana and Dzivarasekwa). The clinics mainly serve people from poor households. BRIDH is located in Mbare residential suburb which is one of the oldest and most impoverished residential suburbs in Zimbabwe.

**Aim 1 and 2: To determine viral load fluctuation between routine annual VL testing and the extent to which annual VL using DBS reflects short term fluctuations that occur in the interim and to determine what proportion of ALHIV with viral load <1000 copies/uL on DBS have a plasma VL less than 200 copies/uL**

The study will explore the sensitivity of viral load testing so that decisions can be made on the best use of resources in optimizing the care and support that can be given to ALHIV in the region. This component will utilize primary and secondary data. Three hundred ALHIV with a recent VL<1000 copies/uL will be randomly selected from clinic registers complete a structured questionnaire. Interviews will explore demographic characteristics, self-reported ART adherence and knowledge of U=U. In depth analysis of ALHIV' VL trajectories will be conducted on a randomly selected sub sample of 100 ALHIV using 6 monthly finger prick DBS and plasma VL sampling to provide evidence on the fluctuation in an individual's virological response over 12 months and how this differs between those considered virologically suppressed (<1000 copies/uL) and those undetectable and untransmissible (<200 copies/uL). Secondary data will be collected from clinic records on HIV treatment history, drug regimens, VL testing (include VL at enrolment and 12 months).

**Aim 3: To explore the reasons for and adolescent's understandings of fluctuations in VL (measured using standard of care DBS) and what a VL<1000 copies/uL means to ALHIV.**

A purposive and theoretical subsample of 20 ALHIV will be selected to participate in longitudinal qualitative interviews at enrolment, 6 and 12 months after receiving their VL result. The subsample will be selected from the quantitative sample. Theoretical sampling is defined as interviewing directed by evolving themes rather than focusing on predetermined populations. Purposive and theoretical sampling are strategies employed to ensure that the participants involved have a wide range of experiences, relevant to answering the research question, but also limit the scale of the data collection so that detailed analyses could be conducted. Interesting dynamics such as duration on ART, current regimen (first/second line), mode of transmission among other things will be considered among other characteristics.

Interviews will explore reasons for consistent/fluctuating VL and their understandings of why and what is happening. We will explore whether having a VL<1000copies/uL motivates them to adhere and whether and how learning that they have a fluctuating or high VL affects their subsequent motivation to adhere and or their wellbeing, as well as the influence, if any, on their experience of HIV stigma. The interviews will also explore what being undetectable means for ALHIV and what influence it has, if any, on their adherence motivation and behaviour alongside developing a broader understanding of the effects of social context, including events in their daily life, on their engagement with and adherence to ART and their understandings of the social meanings of living with HIV. These in-depth interviews will also explore whether and how learning that they have a fluctuating or high VL affects their subsequent motivation to adhere and or their wellbeing, as well as the influence, if any, on their experience of HIV stigma. Interpretations of how the VL results are described to ALHIV by clinic staff will also be explored. Data collection will be an iterative process, where all the interviews will be transcribed and translated in order to inform individualized guides for subsequent in-depth interviews.

**Aim4: To explore the perceived risks and opportunities of incorporating U=U into routine HIV treatment and care for ALHIV in LIC**

Up to four participatory workshops will be conducted with healthcare workers and ALHIV to explore perceived risks and opportunities of incorporating U=U into routine treatment and care for ALHIV in LIC. It is well documented that adolescents' understanding and acceptance of their HIV status and engagement in their treatment is also critical to attaining U=U. The workshops will unpack some of the key challenges that undermine ALHIV's engagement. The first two workshops will be with policy makers to discuss the findings and explore their perceptions on the feasibility of implementing policies related to U=U in this age group. Additionally, their views will be elicited around whether they consider there is 'safe' U=U messaging for LIC that could be implemented logistically, clinically and socially. The last two workshops will include policy makers, healthcare workers and ALHIV to explore the social understandings of and the health system response to the role of undetectable VL results in supporting care to ALHIV.

**Aim 5: To explore with key stakeholders the implications of our findings for the feasibility and framing of the U=U message in LIC for ALHIV.**

Working with the Ministry of Health and Child Care to develop locally appropriate ways of incorporating U=U into routine HIV treatment and care among ALHIV in Zimbabwe. I have already set up a technical working group comprising members from the MoHCC, Africaid Zvandiri and UNICEF. This was made possible through a UNICEF supported small-scale resource development project which is supporting development of resources for ALHIV to improve their HIV literacy and particularly their literacy related to viral load testing, which has been relatively recently introduced into routine HIV care in Zimbabwe. The UNICEF supported project aims to increase understanding about the importance of achieving, monitoring and maintaining viral suppression primarily for prevention of disease progression but also for prevention of mother to child transmission and potentially sexual transmission. Although UNICEF is supporting the small project viral load data will not be collected so the messaging will largely relate to understanding what viral load means rather than whether U=U is a valid message to promote. The study proposed here will provide opportunity for more in-depth exploration of issues and generation of biological evidence to support or refute perceptions and be integrated into materials so that the messaging is clinically sound for what is feasible and deliverable in the Zimbabwean context (and potentially other similar settings within the region).

This study will benefit from the technical working group established as part of the UNICEF project. The participatory workshops will include members from the technical working group and other key stakeholders (policy makers and healthcare workers) to discuss the findings from ALHIV interviews and explore their perceptions on the feasibility of implementing policies related to U=U in this age group. Additionally, their views will be elicited around whether they consider there is 'safe' U=U messaging for LIC that could be implemented logistically, clinically and socially. The workshops will explore the social understandings of and the health system response to the role of undetectable VL results in supporting care to ALHIV, which may or may not include the feasibility of adopting and adapting the U=U message in the Zimbabwean context. We aim to establish the implications of the health systems variation in provision of VL testing between clinics with or without onsite VL. A range of methodological approaches will be used.

## Procedures

### Quantitative interviews

The sample size for ALHIV will be calculated with reference to the total number of ALHIV aged 13-19 years on ART with a VL <1000copies/uL taken within 6 weeks of study launch from the 3 sampled clinics according to the clinic records. A list of all ALHIV aged 13-19 on ART will be drawn from the ART registers from this, a systematic random sample will be selected to recruit 300. The sample sizes will be calculated using a margin of error of 5 %; confidence interval of 95% and response distribution of 50% (<http://www.raosoft.com/samplesize.html>). The figure obtained will be shared among the 3 clinics using Probability Proportionate to Size (PPS) sampling. ALHIV taking account age, recency of disclosure, duration on ART and current ART regimen and will be shared among the three clinics using Probability Proportionate to Size (PPS) as in figure 1 below.

[figure not shown]

Figure 1: Recruitment flow chart

The quantitative subset of 100 ALHIV who will have intensive follow up and will provide plasma and DBS samples VL testing at enrolment, 6 and 12 months will be randomly selected. Ideally, we wanted to have intense follow up on all 300 participants however due to limited resources we reduced the sample size for intense follow up to 100 participants.

Eligible participants will be drawn from the clinic records with the assistance of the clinic nurses. A list of potential eligible participants per clinic containing the residential suburb, name and contact details will be given to the Africaid Zvandiri Community Adolescent Treatment Supporters (CATS) working in the clinics for recruitment during regular support group meetings or through the phone. CATS are ALHIV aged 18-24 years who are trained by Africaid and MOHCC to provide support to other ALHIV. All the clinics are supported by Africaid and offer psychosocial support services to ALHIV through a combination of home visits and support groups. Willing participants will be invited to the clinic and will be introduced to the research team. After being given study information, interested participants who met the inclusion criteria and willing to provide written informed consent were recruited.

Subject to feasibility, all interviews will be conducted in ALHIV's HIV clinics in private and conducive interview rooms. In exceptional cases, where the public sector clinics have limited space interviews will be conducted at the CeSHHAR office. All participants and their parents/caregivers will be reimbursed for their transport costs and given a token of appreciation in line with local ethics committee guidelines for participating. Where possible interviews will be scheduled around the same time ALHIV attend their routine clinic visits to minimise visits to the clinics. No direct household or community contact will be

made by the research team in order to avoid inadvertent disclosure of their HIV status and to prevent the risk of stigma and discrimination of participants.

Participants will complete a structured questionnaire using Audio Computer-Assisted Self- Interview (ACASI) at enrolment and after 12 months. Interviews will explore demographic characteristics, self-reported ART adherence, changes in treatment and illness and knowledge of U=U. Data will be collected from clinic records on HIV treatment history, drug regimens, routinely collected VL results.

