**The specific objectives are:**

1. To determine viral load fluctuation between routine annual VL testing and the extent to which annual VL using DBS reflects short term fluctuations that occur in the interim.
2. To determine what proportion of ALHIV with VL <1000 copies/uL on DBS have a plasma VL less than 200 copies/uL
3. To explore the reasons for and adolescent's understandings of fluctuations in VL and what a VL<1000 copies/mL means to ALHIV

**Methods:** This mixed method study will be conducted in conjunction with key stakeholders. We will enrol 300 ALHIV with a recent VL<1000 copies/uL in three HIV clinics in Harare and follow them for 12 months. Of these, 100 will be randomly selected to undergo repeat VL testing, using both DBS and plasma samples at enrolment, 6 and 12 months. A purposive sample of twenty will be selected for a longitudinal qualitative study. Additionally, up to eight participatory workshops will be conducted with key stakeholders over the course of the study to co-develop a 'safe' way to message U=U for LIC.

**Potential impact:** The study will provide scientific evidence on whether routine VL testing using DBS as available in LIC can provide sufficiently robust evidence of 'undetectability' and on the variability of an individual's virological response over 12 months. It will provide contextually orientated evidence to inform U=U messaging which has the potential to change the motivation of ALHIV to engage with their treatment and care.

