### Aim

The study aims to provide scientific evidence on whether routine VL testing using DBS as available in LIC can provide sufficiently robust evidence of 'undetectability' and on the variability of an individual's

virological response over 12 months and between those considered undetectable (<1000) and those undetectable and untransmissible (<200). We therefore propose to conduct a longitudinal study to i) determine at what 'threshold' U=U might be safely promoted in this setting; ii) explore ALHIV's understanding and or interpretation of the VL results. The study will also explore responsible ways to disseminate this message to ALHIV living in Zimbabwe, and across the Southern African region.

Our specific objectives are:

1. To determine viral load fluctuation between routine annual VL testing and the extent to which annual VL using DBS reflects short term fluctuations that occur in the interim.
2. To determine what proportion of ALHIV with viral load <1000 copies/uL on DBS have a plasma VL less than 200 copies/uL
3. To explore the reasons for and adolescent's understandings of fluctuations in VL (measured using standard of care DBS) and what a VL<1000 copies/mL means to ALHIV
4. To explore the perceived risks and opportunities of incorporating U=U into routine HIV treatment and care for ALHIV in LIC
5. To explore with key stakeholders the implications of our findings for the feasibility and framing of the U=U message in LIC for ALHIV.

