### Responsibilities

Data management will take place at CeSHHAR Zimbabwe led by JD under the direction of principal applicant. The principal applicant and research team will be responsible for ensuring good quality data are collected.

**Data analysis:** Quantitative data will be analysed using STATA 15.0. Descriptive summaries and frequencies of social, clinical and demographic characteristics by different VL trajectories will be conducted. All qualitative interviews will be conducted by the PI in Shona, audio-recorded, transcribed verbatim, and translated into English. Iterative data collection and analysis will be conducted. Preceding interviews will inform subsequent interviews. Data will be uploaded, coded and summarized using a qualitative software package (NVivo 9.0, QSR International). Data analysis will be conducted using thematic and constant comparison analytical approaches (23). In the initial stages I will adopt a thematic approach to explore emerging themes followed by adopting a constant comparison approach within and across and between different participants.

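### Does the 5% margin set for the cohort of 300 leave Objective 2, which rests on only 100 participants, wrongly planned?

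*Combined protocol and SAP*

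**What the plan says.** The sample-size paragraph under Procedures, Quantitative interviews, refers to a systematic random sample from the ART registers: "a systematic random sample will be selected to recruit 300". The precision inputs come next: "The sample sizes will be calculated using a margin of error of 5 %; confidence interval of 95% and response distribution of 50" per cent. The result is then allocated to sites: "The figure obtained will be shared among the 3 clinics using Probability Proportionate to Size (PPS) sampling".

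The smaller sample has its own paragraph in the same section. The team says it would have liked intensive follow-up of all 300, but "due to limited resources we reduced the sample size for intense follow up to 100 participants".

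Objective 2, under Aim, is: "To determine what proportion of ALHIV with viral load <1000 copies/uL on DBS have a plasma VL less than 200 copies/uL". It needs a DBS and a plasma result from the same person. The Abstract says who provides them: "100 will be randomly selected to undergo repeat VL testing, using both DBS and plasma samples at enrolment, 6 and 12 months". Study design and setting agrees, describing a "randomly selected sub sample of 100 ALHIV using 6 monthly finger prick DBS and plasma VL sampling".

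For analysis, the Data analysis paragraph under Responsibilities says: "Descriptive summaries and frequencies of social, clinical and demographic characteristics by different VL trajectories will be conducted". It names no interval for Objective 2 and does not say whether the three visits are reported separately or together.

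**The concern.** The only margin of error a reader can find is 5 points, and it comes from a calculation for a different sample. Objective 2 is the quantitative core of the question whether a DBS result below 1000 can support U=U messaging, and a third of the cohort answers it. If someone carried the 5% across, the Objective 2 result would look about twice as precise as it is in the worst case.

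The direction of the error matters too. The group of concern has a DBS result below 1000 but plasma VL of 200 or above. If 10 of 100 fell there (an assumed count), the Wilson 95% interval would run from 5.5% to 17.4%. A bare 10%, read as good to 5 points, would hide the upper part of that range from the policy makers and clinic staff for whom the findings are meant.

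**Working it through.** **Inputs.** From Procedures, Quantitative interviews: margin E = 0.05, 95% confidence (z = 1.96), p = 0.50, cohort 300, paired subsample 100. The size N of the eligible pool is named as an input, but the text gives no number for it (Figure 1 is not shown in the copy reviewed). Simple random sampling is assumed throughout.

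**1. The plan's own 300.** Without finite-population correction, n = z²p(1−p)/E² = 0.9604/0.0025 = 384.2, so 385. With correction, n = Nx/((N−1)E² + x), where x = z²p(1−p) = 0.9604. This rounds up to exactly 300 for N between 1,346 and 1,366. So 300 is consistent with the stated inputs for a pool of roughly that size, but cannot be confirmed without N. Nothing shows it to be miscalculated.

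**2. Could the 5% also cover the 100?** The wording speaks of sample sizes in the plural. For n = 100 at p = 0.50 the uncorrected margin is 1.96 × √(0.25/100) = 9.8 points. Correction would have to shrink this to 5.0, which requires (N−100)/(N−1) = (5.0/9.8)² = 0.260, so N is about 135. That is fewer than the 300 to be recruited. Even at the smallest possible pool, N = 300, the margin is 9.8 × √(200/299) = 8.0. The 5% therefore cannot describe the 100.

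**3. Margin for each sample, per visit.** Formula: 1.96 × √(p(1−p)/n), uncorrected, in percentage points. The 50% is the plan's input; the other proportions are assumptions.

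| True proportion | n = 100 | n = 300 |
|---|---|---|
| 50% | 9.8 | 5.7 |
| 80% | 7.8 | 4.5 |
| 90% | 5.9 | 3.4 |
| 95% | 4.3 | 2.5 |

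The ratio is √3 = 1.73 in every row. Setting 1.96 × √(p(1−p)/100) = 0.05 gives p(1−p) = 0.0651, so p = 0.93: at about 93% or above, 100 people give a margin within 5 points.

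**4. Finite-population correction.** With N = 1,366 the figures at 50% are 9.8 × √(1266/1365) = 9.4 for 100 and 5.66 × √(1066/1365) = 5.0 for 300. That N was solved so that 300 gives 5.0, so the second figure is true by construction and is no independent evidence. Over pools of 500 to 5,000 the margin for 100 runs from 8.8 to 9.7.

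**5. Denominator and visits.** Only pairs with DBS VL below 1000 count. With 90 or 80 usable pairs (assumed), the uncorrected margin at 50% is 10.3 or 11.0. If the three visits were pooled, the margin would be 9.8 × √((1+2ρ)/3), where ρ is the within-person correlation: 5.7 at ρ = 0, 8.0 at ρ = 0.5 (assumed), 9.8 at ρ = 1.

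**6. What the plan would have to breach.** For Objective 2 the documents state no margin, hypothesis test, power or minimum acceptable proportion. No stated property can be set against 9.8 points and found to fail.

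**The case for a change.** The strongest case for a change is that the remedy is only wording. One sentence would say that the 5% applies to the 300 and give the margin for the 100. Another would have Objective 2 reported at each visit as a count over usable pairs with a 95% interval, allowing for repeated measurements if visits are pooled. The protocol explains why the number is 100 but not what that costs in precision, and Objective 2 will inform policy.

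The factual part of this stands: no precision is given for the 100, and the 5% cannot be borrowed for it. Such sentences would be a reasonable courtesy to readers.

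They would not alter the study, however. The sample of 100 stays as it is, because resources fix it. The estimand is clear from the objective: plasma VL below 200 among those with DBS VL below 1000. Random selection makes the observed proportion a valid estimate. An analyst reporting it would take the interval from the observed counts, so the planning margin for the 300 never enters. Clustering matters only for a pooled estimate, which the plan does not announce, and allowing for repeated measurements on the same person is routine.

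The 9.8 is also a worst case. The 50% is the planning value for the 300, not an expected result for Objective 2, and the margin shrinks as the true proportion rises. Finally, the paragraph on the 100 separates it from the 300 and admits the compromise, so the text does not invite a reader to apply 5% to it.

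**Conclusion.** No change is needed. This is an unstated detail, not an arithmetic error: the 300 is compatible with its inputs, and no margin is claimed for the 100. On a simple random sampling basis without finite-population correction, Objective 2 will carry a per-visit 95% margin of about ±9.8 points at 50% and about ±5.9 if the true proportion is 90% (an assumption), somewhat wider if fewer than 100 pairs have DBS VL below 1000. Choosing 100 rather than 300 for paired testing is a fair trade-off, openly attributed to resources, in a descriptive study with no criterion that the wider margin would breach. This conclusion rests on the 100 being a random draw, as the protocol says, and on the result being reported with its own denominator, as ordinary practice would do. A sentence giving the margin for the 100 is optional and would leave design, estimate and interpretation unchanged.

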### Qualitative interviews

The longitudinal qualitative subsample of 20 participants will be theoretically selected from the baseline cohort. As part of the mixed method study design, the quantitative analysis will inform the dimensions of the qualitative sample. Key sampling characteristics which emerge as being pertinent for inclusion and exploration within the qualitative sample will be identified from the quantitative analysis. Household circumstances, duration on ART, current regimen (first/second line), mode of transmission may be considered among other characteristics. Theoretical sampling is based on specific characteristics and directed by evolving themes rather than focusing on predetermined populations (25). Our sampling will ensure participants have a wide range of experiences, relevant to answering the research questions.

A sample of 20 participants for in-depth qualitative studies is anticipated to be large enough to ensure a broad coverage of the specific questions and to ensure theme saturation. Given the interview design (enrolment, 6 and 12 months), the proposed sample size (20 x 3 phases) will enable the quantity of data collected to remain manageable (n=60 interviews) within the timeframe to allow thorough and rich analyses. The longitudinal approach will allow the study to capture changes over time with regards to how adolescents understand VL testing. Eight (8) participatory workshops will be conducted with 20 key stakeholders including healthcare workers with direct contact with the ALHIV and have been involved in viral load results counselling and participating clinics.

